11.3 Exploratory Endpoints

The exploratory endpoints are:

- Hospital LOS (number of days in the hospital, evaluated in hours) will be measured first by time to discharge order is written. The time will start at time of surgical closure and run until discharge order is written.
- Pain values, evaluated using
 - Values recorded from the NPRS
 - Analgesia consumption, including totals for opioid use and morphine equivalents
 - See Section 15 APPENDIX A for conversion guidelines
- The number of subjects with recorded bowel obstructions (Listing only)
 - AE Preferred Terms having the phrase "bowel obstruction" in them e.g., small bowel obstruction
- The number of subjects with a hospital re-admission
- Blood product transfusion volume on the day of surgery (Listing only)

The following LOS parameters will also be evaluated:

- Time from surgical closure to actual discharge
- Time from surgical closure to standard discharge (Listing only) The time will start at time of surgical closure and run until all four criteria for discharge have been met. The criteria are:
 - Passage of stool
 - Ability to tolerate solid food and drink comfortably
 - Adequate oral analgesia, and
 - Subject's willingness to be discharged

Selected time-to-event endpoints (See Table in Section 11.5) will be analyzed using a stratified Cox PH model with treatment as the main effect, stratified by surgery type (laparotomy versus minimally invasive). Comparison of treatment groups and assessment of the significance of the

parameter estimates for surgery type will be made using the Wald chi-square test. In addition to the semi-parametric Cox PH model, non-parametric Kaplan-Meier survival curves will be produced for the two treatment groups and compared using a stratified log-rank test. The number of hours to each endpoint will be presented in summary tables with descriptive statistics for the mITT and PP populations.

Pain assessments will be collected daily from surgery (Day 0) through post-operative Day 14 (or for as long as the patient remains hospitalized), at hospital discharge, and at the second surgery.

All exploratory endpoints will be summarized by treatment group, except where it is indicated that only a listing will be provided. For continuous endpoints, summary statistics (n, mean, SD, minimum, first quartile, median, third quartile, maximum) will be presented for the mITT population, with comparisons of means made using the van Elteren test (Justification previously provided in Section 11.1.1.) For categorical endpoints, counts and percentages will be presented for the mITT population, with comparisons of proportions made using CMH with Wald 90% CIs (Justification previously provided in Section 11.1.111.1.1).

All results will be listed for the mITT population, including calculated time to event efficacy variables.

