6.11. Opioid Use

The use of opioid pain medications will be collected daily from Screening through Day 14, and at Hospital Discharge or study termination, whichever comes first.

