Synopsis – Exclusion Criteria	
 Removed exclusion 5 'insulin dependent diabetes mellitus' Removed exclusion 8 'risk factors for thromboembolic events' Removed exclusion 11 'body mass index (BMI) > 40' Removed exclusion 16 'chronic opioid usage' Added new exclusion 7 'has peritoneal carcinomatosis' 	
 For the removal of exclusion criteria 5, 7 and 11, these were removed to align this with the recently cleared phase 3 'INTEGRITY' clinical trial Chronic opioid usage was removed as the study is enrolling only subjects that require a stoma and the primary endpoint is assessing adhesions per amendment 4 Added exclusion criteria 7, has peritoneal carcinomatosis, as this would not be suitable subject to receive study drug
Synopsis – Perioperative Standardization of Care	
 Removed NPO and updated with 'Anything by mouth' 	
 The lead-in sentence started with 'not' so removed the double negative
3.1 Overall Study Design and Plan	
 Updated ¶2, 1st sentence to reflect when randomization should occur (Day -1 instead of Day 0) 	
 Reflects the timing per the Schedule of Assessments when the site should randomize a subject
3.2 Perioperative Standardization of Care	
 Removed NPO and updated with 'Anything by mouth' 	
 The lead-in sentence started with 'not' so removed the double negative
4.3 Exclusion Criteria	
 Removed exclusion 5 'insulin dependent diabetes mellitus' Removed exclusion 8 'risk factors for thromboembolic events' 	
 For the removal of exclusion criteria 5, 7 and 11, these were removed to align this with the recently cleared phase 3 'INTEGRITY' clinical trial

Section	Change	Rationale
	
 Removed exclusion 11 ‘body mass index (BMI) > 40’ Removed exclusion 16 ‘chronic opioid usage’ Added new exclusion 7 ‘has peritoneal carcinomatosis’ 	
 Chronic opioid usage was removed as the study is enrolling only subjects that require a stoma and the primary endpoint is assessing adhesions per amendment 4 Added exclusion criteria 7, has peritoneal carcinomatosis, as this would not be suitable subject to receive study drug

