Selected time-to-event secondary efficacy endpoints (See Table in Section 11.5) will be analyzed using a stratified Cox PH model with treatment as the main effect, stratified by surgery type (laparotomy versus minimally invasive). In addition to surgery type, a categorical age (<65 years, ≥ 65 years) will be included. Nominal p-values will be reported. Comparison of treatment groups and assessment of the significance of the parameter estimates for surgery type will be made using the Wald chi-square test.

In addition to the semi-parametric Cox PH model, non-parametric Kaplan-Meier survival curves will be produced for the two treatment groups and compared using a stratified log-rank test; results from this test will be considered nominal/hypothesis-generating in nature. The number of hours to each endpoint will be presented in summary tables with descriptive statistics for the mITT (all variables selected) and PP populations (POI, GI2, and GI3 variables only).

Those endpoints defined as yes/no variables will be analyzed using a chi-square test for homogeneity of proportions.

All findings will be presented in subject listings for the mITT population, including calculated time to event efficacy variables.

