17 REVISIONS TO STATISTICAL ANALYSIS PLAN

Date	Revision
October 11, 2022	Version 2.0: Extensive revisions reflect the changes made to the study protocol covering Amendments 4, 5, and 6. The most significant change was the in the designation of the primary endpoint. The primary endpoint was changed from the number of hours from surgical closure to return of GI function as measured by GI2 to compare the change from baseline in extent and severity of intra-abdominal adhesions among subjects treated with LB1148 or placebo. Another significant change increased the alpha to 0.10 and changed the CIs from 95% to 90%.
March 10, 2023	Version 3.0: The following statement was returned to this version of the SAP. “All statistical tests will be 2-sided, with p-values considered nominal. A p-value < 0.05 will be highlighted.” Gender and BMI added to models in specific efficacy analyses. An analysis was added regarding time between drug administration and actual surgery start time and efficacy between the two treatment groups. Confidence intervals were changed from 90% back to 95% throughout. Cocclini scoring system added to the primary endpoint. One shift table was added to better display the change in number of adhesions between the two surgeries.

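### Chronic opioid users are now eligible, but the opioid-total and bowel-recovery comparisons take no account of recorded pre-operative opioid use; the tests stay valid but may lose precision

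*SAP*

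**What the plan says.** **Eligibility.** The exclusion list in Protocol 4.3 has no criterion on chronic opioid use. The Amendment 6 entry in Protocol Appendix 9 (26 August 2022) explains: "Chronic opioid usage was removed as the study is enrolling only subjects that require a stoma". It adds a second reason, that the primary endpoint now assesses adhesions.

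**Data collected.** Protocol 6.11: "The use of opioid pain medications will be collected daily from Screening through Day 14". Protocol 6.5 records concomitant medications from 2 weeks before randomization.

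**Opioid analysis.** SAP 11.3 evaluates pain partly through "Analgesia consumption, including totals for opioid use and morphine equivalents". Continuous exploratory endpoints are analysed "with comparisons of means made using the van Elteren test". The only stratification factor that the SAP describes for this test is surgery type (SAP 11.1.1). No time window is set for the totals.

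**Bowel-recovery analysis.** SAP 11.2.2 uses a Cox model with treatment as the main effect, stratified by surgery type. It then says: "In addition to surgery type, a categorical age" (under 65, or 65 and over) is included. The SAP revision history (section 17) notes "Gender and BMI added to models in specific efficacy analyses". Opioid use is not named there either.

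**Status.** SAP 4.2 makes all p-values nominal and two-sided, with values below 0.05 highlighted.

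**The concern.** Pre-operative opioid use is in effect the baseline value of the opioid-consumption outcome. A habitual user is likely to keep consuming after surgery for reasons unrelated to LB1148. Protocol 1.2 also lists narcotics among the mechanisms of ileus, so prior use may plausibly affect GI2, GI3 and the other recovery times.

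The reasons given for lifting the exclusion concern the stoma-only population and the adhesion endpoint. They do not address bowel function (secondary objectives) or pain and opioid consumption (exploratory), all of which were kept. I found no opioid covariate, stratum, subgroup, change score or sensitivity analysis in the SAP.

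If chronic users are present, their habitual intake adds variance to these comparisons. In a sample this small, an uneven split between arms can also move the result.

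**Working it through.** **Plan figure to reproduce.** None. SAP 4.3 states that no power calculations were used. Everything below on size is illustration on assumed inputs.

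**Inputs from the documents.** At least 30 randomized (SAP 4.3) at 1:1 (Protocol 5.4) gives 30 / 2 = 15 per arm. Tests are two-sided, with 0.05 highlighted (SAP 4.2).

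**Assumed inputs.** Chronic users are 10%, 20% or 30% of subjects. Post-operative opioid totals are log-normal with log-SD 0.7. LB1148 halves opioid use. How far habitual use carries over is varied below.

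**Step 1: chance imbalance.** With X and Y independent Binomial(15, p), the exact probabilities are:

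| Prevalence p | P(arms differ by 2 or more users) | by 3 or more | by 4 or more |
|---|---|---|---|
| 10% | 35% | 12% | 3% |
| 20% | 49% | 25% | 11% |
| 30% | 55% | 32% | 16% |

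If a user carries over 60 MME/day for 5 days, each extra user moves an arm's mean by 60 × 5 / 15 = 20 MME, against an assumed non-user median of 100 MME. This affects the tabulated means directly. The van Elteren test works on ranks and is less sensitive to it.

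**Step 2: validity.** With no drug effect, 15 or 20 per arm, and users taking 2, 3 or 5 times what others take, the test stratified by surgery type alone rejected in 4.5% to 5.4% of 4,000 simulated trials per setting. When only trials whose arms differed by 4 or more users were counted, the rate was about 7% to 20%. The test is therefore sound on average but can mislead in an unlucky allocation.

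**Step 3: power for opioid totals, 15 per arm.** Each cell shows the planned test, then the analysis that accounts for prior use.

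| Carry-over model | 10% users | 20% users | 30% users |
|---|---|---|---|
| Users take twice what others take | 66% / 66% | 62% / 64% | 61% / 64% |
| Users take 5 times as much (stratified by yes/no use) | 55% / 65% | 47% / 64% | 39% / 63% |
| Habitual 300 MME fully added, untouched by drug, known exactly | 51% / 64% | 36% / 58% | 25% / 55% |

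The gain is about 0 to 3 points in the first row. In the last it is 64 − 51 = 13, 58 − 36 = 22 and 55 − 25 = 30 points. The result is driven by the carry-over model as much as by prevalence.

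**Step 4: GI2.** The Cox model was simulated with 30 subjects, 1,500 trials per setting, treatment hazard ratio 2.2, 10% to 25% users, and a hazard ratio for users of 0.4 to 0.5. Power without and with the opioid term was 43.3% / 45.2%, 40.1% / 44.8% and 39.2% / 46.7%, a gain of about 2 to 8 points. The Monte Carlo standard error of one estimate is √(0.44 × 0.56 / 1500) ≈ 1.3 points, so the smallest gain is hardly distinguishable from none.

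**Step 5: can the baseline variable be derived?** A yes/no flag can be taken from the 14-day medication record (Protocol 6.5; Appendix 1, footnote 6). Pre-operative MME/day is less certain, for three reasons:
- Screening and Day 0 may be the same visit (Appendix 1, footnote 1), so daily collection from Screening may leave almost no pre-operative record.
- Protocol 5.6 asks for the dates of concomitant medications, and neither 5.6 nor 6.5 mentions dose.
- SAP Appendix A gives buprenorphine no conversion factor, so a buprenorphine user could score zero.

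**The case against.** The strongest reply is that this is a preference and not an error. Allocation is randomized, p-values are nominal, and the stated aim is to explore the feasibility of the adhesion endpoint. Power for an exploratory pain item is not a design target, and many other prognostic factors also go unadjusted. That stands, and it limits the point to an optional gain in precision.

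The size is also uncertain, and this stands too. The large power gains need habitual intake to be added in full, unaffected by treatment and measured exactly. Prevalence may be diluted as well: the mITT population starts on 01 January 2022 (SAP 4.1), whereas Amendment 6 is dated 26 August 2022, so some subjects may have been enrolled while the exclusion applied.

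It can also be said that medications are tabulated by arm (SAP 9), so gross imbalance would show. This stands only in part. A chronic user still taking opioids at the first dose is classed as concomitant, in the same category as opioids started after surgery. The tables do not isolate chronic users and do not enter any comparison.

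A reader might infer that the planned comparisons are biased, or that the exclusion was lifted for the adhesion endpoint alone. The documents support neither: allocation is randomized, with simulated error near 5%, and Amendment 6 gives two reasons.

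**Conclusion.** The point holds as a minor improvement. Chronic opioid users are eligible, their prior use is recorded, and neither SAP 11.3 nor SAP 11.2.2 uses it. The planned tests remain valid under randomization. What is lost is precision, together with some protection against a misleading result when about 15 per arm are unevenly split.

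The size cannot be fixed from the documents. It runs from negligible (few users, or users taking about twice what others take) to substantial for opioid totals (habitual dose fully added), and it is modest for GI2. A reader might also infer that adjustment removes the problem. It does not: in the full carry-over model, adjusted power still falls from 64% to 55% as prevalence rises from 10% to 30%.

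The missing time window for the opioid totals should be settled first. Collection starts at Screening, so a literal total could include pre-operative intake. None of this bears on who should be eligible.

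**What to change.** **SAP 11.3**
- Define the opioid and MME totals as use after surgical closure, and state when the window ends.
- Derive a yes/no flag for any opioid use, including buprenorphine, in the 14 days before randomization.
- Report a rank-ANCOVA stratified by surgery type, with that flag as covariate, beside the planned van Elteren test. Pre-operative MME/day may replace the flag where dose is recorded.

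**SAP 11.2.2**
- Add the flag beside age as a pre-specified sensitivity analysis of the GI2, GI3, bowel-movement and solid-diet Cox models. Keep the planned models as they are.

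**Cost.** SAP wording, one derived variable and a few extra output lines, with no new data collection for the flag. The downside is one more parameter with about 30 subjects, and little gain if users turn out to be few. The change should be made before unblinding, because an adjustment added later would look data-driven.

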6.5. Concomitant Medication Assessments

Concomitant medications, including prescription and over-the-counter drugs, will be recorded within 2 weeks prior to randomization through Post-Operative Day 14, and at Hospital Discharge, or study termination, whichever comes first. Additionally, any perioperative surgical preparation that was given or consumed will be documented, including mechanical bowel prep and nutritional supplements (refer to [Section 3.2](#), [Section 5.6](#), and [Section 0](#)).

Blood products administered to the subject will be documented throughout the same timeframe on the Concomitant Medication eCRFs. Documentation will include start and stop dates and reasons for the use.

Unless otherwise specified in the protocol, administration of other concomitant investigational drugs or devices for any indication, other than study drug, is not permitted while on study. Additionally, receiving medication with TXA while taking the study drug is prohibited along with receiving pancreatic enzyme replacement therapy. Any therapeutic or surgical procedures performed during the study period will be documented. Documentation will include information regarding the date(s), indication(s), description of the procedure(s), and/or any clinical or pathological findings.

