7.1. Adverse Events

An AE is any untoward medical occurrence in a subject administered a drug or biologic (medicinal) product; the event does not necessarily have a causal relationship with the administration of the study drug. An AE can therefore be any unfavorable and unintended sign (including a clinically significant abnormal laboratory finding), symptom, or disease temporally associated with the use of a study drug, whether or not considered related to the study drug.

This includes any side effect, injury, toxicity, or sensitivity reaction, and may include a single symptom or sign, a set of related symptoms or signs, or a disease. An AE may also be any laboratory abnormality judged to be clinically significant by the Investigator that worsened when compared to baseline.

AEs include the following:

- All suspected adverse drug reactions.
- All reactions from medication overdose, abuse, withdrawal, sensitivity, or toxicity.
- Apparently unrelated illnesses, including the worsening of a pre-existing illness.
- Injury or accidents.
Note: If a medical condition is known to have caused the injury or accident (e.g., a fall secondary to dizziness), the medical condition (dizziness) and the accident (fall) should be reported as 2 separate AEs.
- Abnormalities in physiological testing or physical examination (findings that require clinical intervention or further investigation beyond ordering a repeat [confirmatory] test).

- Laboratory abnormalities that are clinically significant and require clinical intervention or further investigation (beyond ordering a repeat [confirmatory] test) unless they are associated with an already reported clinical event.

An AE **does not** include:

- Medical or surgical procedures (e.g., surgery, endoscopy, tooth extraction, transfusion); the condition that leads to the procedure is an AE.
- Pre-existing diseases or conditions present or detected at screening/baseline that do not worsen in severity or frequency.
- Situations where an untoward medical occurrence has not occurred (e.g., hospitalization for elective surgery, social and/or convenience admissions).
- Overdose of either study drug or concomitant medication without any signs or symptoms.

Throughout the course of the study, every effort should be made to remain alert to possible AEs. Subjects should be encouraged to report AEs spontaneously or in response to general, non-directed questioning.

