3.3 Exploratory Objectives

The exploratory objectives of this study are to determine if LB1148 reduces the:

- Post-operative abdominal pain (first surgery only)
- Incidence of bowel obstruction through 30 days post-operatively (first surgery only)
- Incidence of hospital re-admittance through 30 days post-operatively (first surgery only)
- Volume of blood product transfusions needed on the day of surgery (first surgery only)

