11.2.2 Bowel Function Endpoints

The secondary efficacy endpoints include the number of hours from surgical closure to resolution or presence, as appropriate, of:

- Achievement of GI2, defined as the toleration of solid food (subject finished a meal that required chewing and experienced no significant nausea/vomiting for four hours) and the

recovery of the upper and lower GI tract (first bowel movement; passage of stool) following surgery (the time the last skin staple or suture was placed by the surgeon)

- Nausea with a Verbal Rating Score (VRS) ≥ 3 (moderate to severe) (Listing only)
- Vomiting or retching* (Listing only)
- Presence of flatus (Listing only)
- Bowel movement (presence of stool from anus or ostomy)
- Insertion and reinsertion of nasogastric (NG)/orogastric (OG) tube*
 - Removal of NG/OG tube* (Listing only)
- Ability to tolerate a liquid oral diet (liquid diet ordered, and subject is able to sustain oral liquid intake without need for IV fluid administration for hydration)
- Ability to tolerate a solid oral diet (solid food ingestion without significant nausea/vomiting for four hours)
- Achievement of GI3, identical to GI2 except recovery of the upper and lower GI tract is defined by either bowel movement or flatus
- Resolution of POI, defined as having resolved when all of the following criteria are met:
 - Absence of nausea AND vomiting for 12 hours without a NG/OG tube
 - Ability to tolerate a solid or liquid oral diet
 - Passage of flatus OR stool over the preceding 24 hours

The following POI parameters will also be evaluated:

- Incidence of POI (Within 14 days of first surgery, After Discharge), defined as the greater than expected inability to tolerate liquids or solids during the post-operative period
 - Within 14 days of first surgery subjects will be identified by AE preferred term (PT) **and** by a confirmatory imaging study within the start/stop dates of the POI
 - The AE PTs are ileus, post-operative ileus, small bowel obstruction, bowel obstruction, partial bowel obstruction, mechanical bowel obstruction, and non-mechanical bowel obstruction
- Incidence of POI after hospital discharge
 - Subjects will be identified by AE PT as listed above

*Vomiting and retching, as well as insertion, reinsertion, and removal of NG/OG tube will be treated as binary (yes/no) variables.

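### Two of the four exploratory objectives, 30-day bowel obstruction and day-of-surgery transfusion volume, have no planned by-arm summary because SAP 11.3 restricts both to listings

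*SAP*

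**What the plan says.** Protocol 2.1.3 and SAP 3.3 word the exploratory objectives as treatment questions: does LB1148 reduce each of four outcomes. Two of them are "Incidence of bowel obstruction through 30 days post-operatively (first surgery only") and "Volume of blood product transfusions needed on the day of surgery (first surgery only").

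SAP 11.3 then gives the output for the matching endpoints: "The number of subjects with recorded bowel obstructions (Listing only") and "Blood product transfusion volume on the day of surgery (Listing only"). The general rule later in that section is: "All exploratory endpoints will be summarized by treatment group, except where it is indicated that only a listing will be provided". The methods that follow it are summary statistics with a van Elteren test for continuous endpoints, and counts and percentages with CMH and 90% Wald limits for categorical ones. They therefore reach pain and re-admission, but not obstruction or transfusion volume.

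Protocol 7.1 lists what is not an adverse event: "Medical or surgical procedures (e.g., surgery, endoscopy, tooth extraction, transfusion); the condition that leads to the procedure is an AE". Protocol 6.5 sends blood products to the Concomitant Medication eCRFs and adds: "Documentation will include start and stop dates and reasons for the use".

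**The concern.** An objective that asks whether a drug reduces something needs at least a by-arm summary. For two of the four questions the SAP stops at a subject listing, while pain and re-admission get a summary and a comparison. No reason is given for the difference. The obstruction endpoint is itself worded as a number of subjects, yet SAP 11.3 produces no such number by arm.

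The documents make both outcomes relevant. Protocol 1.1 places tranexamic acid in the antifibrinolytic class, and Protocol 1.3 names small bowel obstruction as a possible result of adhesions. If only listings are specified, any by-arm tally will be made after unblinding, with the window, population and method chosen at that point.

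**Working it through.** The point rests on text. The documents state no event rate, effect size or power for either endpoint, so there is no planned figure to reproduce.

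**Step 1. Objectives against planned output (SAP 3.3 and 11.3).**

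| Objective | Output in SAP 11.3 |
|---|---|
| Post-operative abdominal pain | By-arm summary, van Elteren test |
| Bowel obstruction to 30 days | Listing |
| Hospital re-admission to 30 days | By-arm counts, CMH |
| Transfusion volume, day of surgery | Listing |

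Two of four have no by-arm output in that section.

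**Step 2. Do other tables fill the gap?**

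- *Obstruction, adverse event tables (SAP 12.1).* These give counts by preferred term and arm, but in the safety population. That population includes subjects treated before 01Jan2022, whom SAP 4.1 leaves out of mITT. The tables are not limited to 30 days, and events related to the second surgery are also collected (Protocol 7, opening text).
- *Obstruction, POI analysis (SAP 11.2.2 and 11.5).* The obstruction terms are in the POI term list, and POI within 14 days gets a frequency table, a Cox model and Kaplan-Meier curves. Obstruction is pooled with ileus there, and the 14-day definition also requires confirmatory imaging.
- *Obstruction, re-admission (SAP 11.3).* This is summarized by arm, but is not specific to obstruction.
- *Transfusion.* It is excluded from adverse events by Protocol 7.1. SAP 9 plans by-arm frequency tables of concomitant medications, and blood products are on those eCRFs. The tables might show use, but not volume and not day-of-surgery use.

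So obstruction has partial by-arm information and transfusion volume has none.

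**Step 3. Can a 30-day obstruction count be complete?** General adverse event collection ends at Day 14, discharge or termination, whichever is first (Protocol 7, opening text). The Day 30 call records readmissions only (Appendix 1, footnote 13). Protocol 7.5 adds POI events after discharge and before Day 30. An obstruction after discharge that led to no readmission and was not reported as POI could be missed. Removing the listing label does not cure this.

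**Step 4. What could a by-arm table show?** SAP 4.3 expects at least 30 randomized subjects from up to 40 enrolled. With 1:1 allocation that is 30/2 = 15 to 40/2 = 20 per arm. The event counts and rates below are assumptions.

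- Exact (Clopper-Pearson) limits: 0/15 has upper limit 1 − 0.025^(1/15) = 0.218. For 3/15 the limits are 0.043 to 0.481.
- Approximate 95% half-width for a difference of 10% against 5%: 1.96 × √(0.10 × 0.90/n + 0.05 × 0.95/n) = 0.188 at n = 15 and 0.163 at n = 20.
- Chance of no events in an arm of 15: 0.95^15 = 0.463 at a 5% rate; 0.90^15 = 0.206 at 10%.
- Power to detect a halving, two-sided 0.05, normal approximation with the exact Fisher value in brackets:

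| Assumed rates | 15 per arm | 20 per arm |
|---|---|---|
| 5% vs 2.5% | 5.4% (0.0%) | 6.1% (0.2%) |
| 10% vs 5% | 7.4% (0.6%) | 8.6% (1.7%) |
| 20% vs 10% | 11.4% (4.1%) | 13.9% (7.2%) |

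- Continuous endpoint, 80% power: standardized difference (1.960 + 0.842) × √(2/n) = 1.02 SD at n = 15 and 0.89 SD at n = 20.

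The useful output is therefore an estimate with an interval, not a test expected to decide the question.

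**The case against.** The strongest reply is that the listing labels are an explicit choice for sparse endpoints in an unpowered proof-of-concept study whose p-values SAP 4.2 calls nominal, and that a table would not settle either question. The second half stands: Step 4 confirms it, and it limits how the added output should be presented. The first half does not explain why the objectives still ask whether the drug reduces these outcomes.

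A reader might also infer more than the documents support:

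- *That the trial cannot answer these questions from its own data.* The label limits planned output, not data. SAP 11.3 lists all results for mITT, and SAP 13 lists everything in the database.
- *That no by-arm count of obstruction exists.* SAP 12.1 and the POI analysis give partial counts.
- *That transfusion volume is not collected.* Protocol 6.5 names dates and reasons but does not claim to list every field. Protocol 2.3.1 names volume as an endpoint, and a listing of volume presupposes capture. The eCRF is not among the documents, so the right step is to confirm.
- *That the plan fails its promise to inform a later trial.* SAP 4.3 makes that promise for the adhesion endpoint only.
- *That transfusion is central to the drug's proposed mechanism.* Protocol 1.4 describes enzyme inhibition in the bowel lumen and not systemically.

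**Conclusion.** The point holds as a mismatch between stated objectives and planned output. Two of four exploratory objectives have no by-arm summary in SAP 11.3. For obstruction, other tables help but do not isolate events within 30 days of first surgery in mITT. For transfusion volume, no by-arm summary is planned anywhere. The weight is modest: the endpoints are exploratory and the primary adhesion analysis is unaffected. The sample-size statements assume 15 to 20 per arm, and the event rates are illustrative because the documents give none.

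There is also a minor, separate wording conflict. SAP 11.2.2 has "Vomiting or retching* (Listing only") and gives removal of NG/OG tubes the same label; the table in 11.5 agrees for both. The footnote in 11.2.2 makes both yes/no variables, and the text after it sends yes/no endpoints to a chi-square test.

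**What to change.** In SAP 11.3, delete the listing-only label from both endpoints and add:

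1. **Bowel obstruction.** n (%) of mITT subjects with a recorded obstruction within 30 days of first surgery, by arm, with an exact 95% CI, using the preferred-term rule already in 11.3. Exact limits suit zero or near-zero counts better than the section's Wald limits. Add a note that capture after discharge is through readmissions and reported POI events, so obstructions without readmission may be missed.
2. **Transfusion.** n (%) transfused on the day of first surgery, and volume by arm with zeros included, using the summary statistics and van Elteren test already in 11.3.

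Label both as descriptive. Confirm that the eCRF captures transfusion volume. Separately, choose one rule for vomiting and NG/OG removal: either keep them as listings and take them out of the yes/no footnote, or drop the label and test them.

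The cost is two short tables, a check of the eCRF and a few words in SAP 11.2.2. The downside is sparse tables with wide intervals, which the descriptive label should make plain.
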